#### 8.1.3 Packaging, Labelling and Supply (re-supply)

The IMD product comes in a USB drive that the professional can download onto a computer or a tablet. The USB comes in a box with instructions for downloading printed in the inside upper flap of the box. Two USBs will be needed for the trial, one per site. Re-supply should not be necessary unless there is a defect with the USB.

Other medical devices used for the trial are the hearing aids. Each hearing aid has its own serial number that can be tracked back to production. These will be shipped to the trial sites. The sites will document which serial numbers that they receive. They will track which serial numbers are given to participants, and they will track that each of those serial numbers is returned to the site.

#### 8.1.4 Storage Conditions

The IMD is stored on the computer or tablet once downloaded and will stay there for the entire study.

The hearing aids should be kept in a locked compartment, and only the site investigator should have access. This is to maintain control over the serial numbers handed out and received back at the site.

The devices are stored in the blister packs which are kept in boxes in a warehouse until shipped. They have a shelf life of years. They should not be exposed to temperatures below -25° and not above 60° Celsius during storage or transport. The storage of these devices is according to standard procedures.

### 8.2 Admini stration of experimental and control interventions

#### 8.2.1 Experimental Intervention

At the first visit the participants will complete a hearing test using standard audiometry performed by the clinician and a screening using the IMD. The standard audiometry is used as a base test for the inclusion/exclusion criteria and as a control measure for the screening results of the IMD. The hearing devices will be programmed using both the RMD and the IMD during the course of the trial. The screening results from the IMD will be used for both fittings to ensure that the acoustic output of both methods is the same. The difference in the fitting process of the RMD and the IMD is the focus of the trial and not the actual output of the hearing aid.

The IMD will present tones from 250 Hz to 8000 Hz, and the participants will indicate when they've heard the tone. The tones are directed into the ears of the participants with supra-aural headphones. The test should take no more than 15 minutes. Depending on the randomization assignment, some participants will then start the fitting portion of the IMD. Hearing instruments will be connected using a wireless neck loop that the subjects will wear. Once the fitting has been programmed into the hearing aids the investigator will place the hearing aids in the subject's ears. The fitting process should not take more than 20 minutes. They will wear the programmed devices for approximately 10 hours per day for an overall time of approximately 20 +/-10 days for the trial. There are no surgical techniques used in the application of this device. It is a non-invasive device.

The study procedure will use a cross over design with two groups. One group will wear the hearing aids fitted with the IMD and one will wear the hearing aids fitting with the RMD. After 10 days they will switch to whichever method they did not have previously. As stated, the device is non-invasive and requires no surgical procedure. The device sound port will be inserted into the ear and the body of the device placed behind the ear each morning by the subjects themselves and removed each night by the subjects themselves. There is minimal training needed for a first time user to learn how to insert a hearing device. The subjects will be given an Instructions for Use booklet that explains how to insert the device and provides further instructions concerning cleaning, battery changing, and warnings.

#### 8.2.2 Control Intervention

The hearing screening results achieved from the IMD will be manually entered into the standard Oasis software for the fitting with the RMD. The hearing aids will be connected to the software using the same wireless neck loop used for the programming with the IMD. The investigator will fit the hearing aids and then place them in the subject's ears.

The subject will then wear the hearing aids for 10 days. The device will be inserted into the ear and placed over the ear each morning by the subjects themselves and removed each night by the subjects themselves. There is minimal training needed for a first time user to learn how to insert a hearing device. The subjects will be given an Instructions for Use booklet that explains how to insert the device and provides further instructions concerning cleaning, battery changing, and warnings.

### 8.3 Dose / Device modifi cations

The IMD will fit the same amount of amplification to the hearing aids as the RMD; therefore, they should not experience any significant negative differences that would make the subjects want to discontinue use of the device. However, if the subject requests to discontinue they can, at any time, remove the hearing aids fitted either with the IMD or the RMD. They will be asked to return the

hearing aids to the site, but their data will still be included in the results for the current study. All data will remain encoded because results are only recorded using the identification code of the subject.

### 8.4 Compliance with study intervention

It is clearly explained to the subjects that during the periods of intervention it is important to the study that they wear the hearing aids. However, it is the responsibility of the subject to place the hearing aids in their ears every morning.

The software monitors the amount of time that the devices are worn. Therefore, it will be noted if the hearing aids from either field trial have not been worn the expected amount of time or if the time worn between trial periods is not similar. If the device has not been worn a sufficient amount of time the data will not be used for the study. The subjects will be asked to return the devices.

### 8.5 Data Collection and Follow-up for withdr awn participants

Withdrawn subjects' data will not be used in any final data analysis or report. Any data that is collected prior to withdrawal will be kept in the data management database. The data will remain encoded because results are only recorded using the identification code of the subject. Withdrawn subjects will have the opportunity to return to the clinic that recruited them for their hearing healthcare needs whether to purchase hearing aids or routine hearing tests.

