### 7.4 Criter ia for withdra wal / discontinuation of participants

Participants are allowed to withdraw from the study at any time and for any reason. They do not have to share the reasons with the investigator. They will be asked to return the hearing aids. If the decision is made by the investigator then they will inform the participant in person that they are no longer needed for the study. Reasons for withdrawing a participant from the study could be for non-compliance during testing, unreliable responses, medical reasons such as an ear infection, or the study may need to be stopped or postponed. Any data gathered from these subjects will be used for the current study. All data will remain encoded because results are only recorded using the identification code of the subject. There will be at least 5 "back-up" test participants to replace those that withdraw or are withdrawn. These are participants that have already been screened and determined to be appropriate for the testing.

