### 10. SAFETY

### 10.1 Medical Device Category C Studies

All adverse events (AE) including all serious adverse events (SAE) are collected, fully investigated and documented in the source document and appropriate case report form (CRF) during the entire study period, i.e. from patient's informed consent until the last protocol-specific procedure, including a safety follow-up period. Documentation includes dates of event, treatment, resolution, assessment of seriousness and causal relationship to device and/or study procedure.

The information on AEs is systematically collected by the clinician at each study visit. They will follow the procedures outlined in SOP-Medical Device Incident Reporting. The subjects are asked to keep a diary and write down any unexpected events. During the regular clinic visits the subjects are then asked questions about the event to gather details and to determine the severity of the event. If a subject reports pain that results in the inability to use the device he will be withdrawn from the study in order to avoid any pain from using the device and to remove partial data from the study. For reports of pain caused by insertion or the dome itself, the problem can be addressed in the clinic. For example, a different style or size of dome can be placed on the hearing aid, and re-training of insertion can be performed with the subject to avoid wrong or forceful insertion of the device. For reported pain they will be advised to not wear the device for 24 hours before resuming use.

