### 11.3 Statis tical criteria of termination of trial

A single statistical analysis is planned once all recruited subjects have completed the protocol (perprotocol). No interim analysis is planned for a test period of 14 days and no "stopping rules" are set from a statistical perspective. PI's and clinician judgement are considered as reliable enough to stop the trial.

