#### 11.4.1 Datasets to be analysed, analysis populations

Analysis population: a single group that had the same treatment (per protocol set).

The included subjects are first time hearing aid users with the same hearing aid model across the population. As hearing loss does not normally fluctuate, we assume that their hearing capabilities are stable over time and that the performance with a hearing aid can be compared over a longer period without any wash out period. Subjects' individual auditory capacities (hearing loss degree, noise tolerance, speech recognition) vary, however the sample is considered as a homogenous population regarding their experience with the RMD. It will be ensured that the acceptance to generic amplification via hearing aids is not tested but an actual evaluation of the difference between the RMD and the IMD. A single assignment treatment will be considered representative of clinical intervention, i.e. when an experienced hearing aid user acquires a new device.

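### The protocol contradicts itself on using withdrawn participants' data and on replacing dropouts, and its only analysis set cannot show whether post-randomisation exclusions matter

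*Protocol*

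**What the plan says.** **Data of participants who leave.** Protocol 7.4, on participants who withdraw or are withdrawn: "Any data gathered from these subjects will be used for the current study". Section 8.3, on those who ask to stop using the device: "their data will still be included in the results for the current study". Section 8.5, on withdrawn participants: "data will not be used in any final data analysis or report"; what was collected before withdrawal stays in the database. Section 10.1 says that a participant whose pain prevents use is "withdrawn from the study in order to avoid any pain from using the device and to remove partial data from the study".

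**Replacement.** Section 7.4 provides at least 5 back-up "test participants to replace those that withdraw or are withdrawn". Section 11.5 says dropouts are not replaced and that extra participants are enrolled from the start instead.

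**Exclusions.** Section 8.4: "If the device has not been worn a sufficient amount of time the data will not be used for the study". It gives no threshold; 8.2.1 mentions about 10 hours per day, as an expectation. Section 11.5 has data removed when the principal investigator has some doubt about their accuracy, especially about understanding of the questionnaires.

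**Analysis set.** Section 11.4.1 names one population, the per-protocol set, and 11.5 restricts analysis to complete cases. The SAP defines no analysis set, missing-data rule or exclusion rule.

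**Daily wear.** Hours per day from the data log are a secondary outcome in Protocol 5.2 and 9.2.2 and in SAP 2.2.2.

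**The concern.** Sections 7.4 and 8.5 cover the same people and cannot both be followed. Two statisticians could lock different datasets and each cite the protocol. The replacement conflict leaves the number enrolled, and who fills a vacated place, equally open.

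The wear and doubt exclusions come after randomisation, and nobody is blinded (6.2.2). With no all-randomised analysis, a reader cannot tell whether they changed the result. Low wear is also a plausible consequence of a fitting the participant likes less, so removing low-wear data takes away part of what the daily-wear comparison is meant to measure. The trial is called exploratory, but 4.1 also calls it a final validation before sale and 4.2 states a non-inferiority aim, so it should be clear whose data count.

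**Working it through.** **1. The passages side by side**

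| Question | One answer | Other answer |
|---|---|---|
| Are withdrawn or discontinued participants' data analysed? | Yes: 7.4, 8.3 | No: 8.5; 10.1 and the complete-case rule in 11.5 lean the same way |
| Are withdrawals replaced? | Yes: 7.4, at least 5 back-ups | No: 11.5, over-enrol instead |

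The statistical section leans towards 8.5, but no text says which section prevails. This part needs no assumption.

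**2. The plan's own power figure**

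Protocol 11.2 and SAP 3.2 give power 0.82 for the three-outcome preference test (w = 0.65, 2 df, N = 24, alpha 0.05). The noncentrality is N x w² = 24 x 0.4225 = 10.14, and the noncentral chi-square power is 0.821, so the figure reproduces. The two-outcome version (w = 0.6, 1 df) has noncentrality 24 x 0.36 = 8.64 and power 0.836, against 0.84 stated.

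If exactly 24 are enrolled and only complete cases are analysed, the three-outcome power is 0.785 with 22 analysed and 0.743 with 20. To keep 24 analysed without replacement, enrolment of 24/(1 - loss) is needed: 27 at 10% loss, 30 at 20%. The plan states no loss rate. These figures concern the preference test, so they are only indicative for the IOI-HA model.

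**3. The wear rule, by simulation**

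Inputs from the documents: SAP 2.1 gives an IOI-HA difference of 3.2 with effect size 0.68 (experienced users) and a non-significant 0.5 in first-time users. If 0.68 was standardised by the SD of differences, that SD is 3.2/0.68 = 4.7 and the within-period SD is 4.7/√2 = 3.32.

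Assumptions, none given in the documents: the lowest 10% or 20% of wear periods are excluded, and the pair with them; the period part of wear correlates 0.3 or 0.5 with that period's benefit; wear in a person's two periods correlates 0.5 or 0.7. Wear = √r x person part + √(1-r) x period part, and under the IMD the period part is shifted by correlation x effect / 3.32.

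Results for r = 0.5-0.7:

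- Pairs lost: 15-32%. From 24 this leaves 24 x 0.85 = 20.4 down to 24 x 0.68 = 16.3, so about 20 to 16 pairs.
- Exactly one usable period, discarded by complete-case analysis: 11-23% of participants.
- SE of the IOI-HA difference: 4.7/√24 = 0.96 with all pairs, 4.7/√20 = 1.05 to 4.7/√16 = 1.18 after the loss.
- IOI-HA estimate: shifted towards zero by under about 0.2 at a true -3.0, by about 0.05 or less at -0.5, and not at all at zero effect.
- Daily-wear difference: about 76-90% of its true size.

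At a true -0.5 removal is nearly equal between fittings (IMD 10-21%, RMD 9-20% over all correlations tried, including zero), so the shrinkage comes from truncation, not from unequal removal.

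**4. A second look in hours**

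Assume a mean of 10 h/day on one fitting, a true difference of -1 h, SD 2-3 h and within-person correlation 0.5-0.8. Requiring 6 h in both periods keeps 79-93% of participants and gives -0.82 to -0.96 h. Requiring 8 h keeps 54-67% and gives -0.70 to -0.87 h. These cut-offs show direction only and are not proposals.

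**The case against.** - **The trial is exploratory, and extra enrolment is planned.** A per-protocol set is not in itself an error, and with 24-40 participants (7.3) over-enrolment can restore precision. That stands. It cannot resolve the contradictions or undo truncation.
- **The figures measure only the wear rule.** Correct: they say nothing about withdrawn data, replacement or doubt removals. The exclusion rate is assumed, and the SD of 4.7 depends on how the reference study standardised its effect size, for a contrast of preferred against less preferred fitting.
- **Worse figures are available.** A reader might infer a wear ratio of 0.58, 36% of pairs lost and 33% with a single usable period. Those need zero correlation between one person's wear in two consecutive periods, an extreme case.
- **The wear log might be kept.** Section 8.4 could be read as sparing the log, and no test is assigned to daily wear, which 11.4.4 also lists among explanatory variables. So truncation follows from the plain reading, not from an explicit statement. Dissimilar wear between periods is only noted; 8.4 does not clearly make it a ground for exclusion.
- **Single usable periods may be fewer.** Section 8.4 goes on to ask for the devices back, and 7.4 lists non-compliance as a withdrawal reason. If removal is of the whole participant, failure in period 1 means period 2 is never observed.
- **The missing criteria are mostly missing detail.** Staff review the questionnaires with participants when issued (9.3.1, 9.3.2), the investigator reviews them on return (9.3.2, 9.3.3), and missing items are sought by post (11.5). This makes removal rarer but supplies no criterion. The audit trail (12.2.2) records changes without setting one.
- **Safety.** A reader might infer from 8.5 that a withdrawn participant's adverse events would go unreported. The documents do not support that: 10.1 requires all adverse events to be documented from consent, 10.1.2 imposes separate reporting, and 12.1.2 requires a case report form for non-completers.

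**Conclusion.** The two contradictions, on data use and on replacement, are certain from the text and should be fixed before the database is locked. The lack of any all-randomised analysis beside exclusions made without blinding is a real weakness of the plan. Plainly read, the wear rule also truncates a secondary outcome on its own value.

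The sizes are less certain, since they depend on an exclusion rate and correlations that the documents do not give. The clearer costs are lost pairs and an understated daily-wear difference. A reader might infer that the IOI-HA comparison is seriously biased; the calculations do not support that for the wear rule, and the effect of doubt removals is unknown. The safety wording is a minor clarification.

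**What to change.** - Reconcile Protocol 7.4, 8.3, 8.5, 10.1 and 11.5 into one data-use rule and one replacement rule, and repeat both in the SAP. The clinical rule for withdrawing a participant is left to the sponsor.
- Run the planned mixed model on all randomised participants with at least one post-period questionnaire, regardless of wear. Report it beside the per-protocol complete-case result, since 4.2 also has a non-inferiority aim.
- Analyse daily wear without the wear exclusion.
- Before analysis, fix the wear criterion, whether it removes a period or a participant, and the reasons for removing a questionnaire. List every removal by sequence and period.
- State that the exclusion in 8.5 does not apply to adverse events.

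**Cost:** wording, one added analysis with a model already planned, and possibly an amendment needing ethics committee and authority approval (2.10). The all-randomised set brings slightly more noise or dilution, which is why it stands beside the per-protocol result and does not replace it.

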#### 8.6 Trial specific preventive measures

The performance of a hearing aid is not impacted by medication. The subjects will continue to take whatever type of medication that they normally take. There will be no impact on the study objectives.

### 8.7 Concomitant Inter ventions (treatments)

Test subjects will continue to receive any concomitant care and medication that they normally receive during the use of the IMD. Use of medication or other therapies will not affect the benefit of the hearing aids. There will be no impact on the study objectives.

### 8.8 Medical Device Account ability

The USB used to download the IMD software into each site's trial specific computer will be tracked with serial numbers. They will be shipped from Poland. Only IMD that are from a tested batch will be used in the study

The subjects will be assigned hearing aids with serial numbers. The serial numbers are tracked when fitted and tracked that they are received back by the sites on the last visit. The devices have serial numbers by which the individual device can be identified and the production history traced. They will be shipped from the production site in Poland. The serial numbers will provide the traceability of their production and from which batch they came.

### 8.9 Return or De structio n of Stud y Drug / Medical Device

At the end of the study the software will be uninstalled from the sites' computers (confirmed by the monitor), and the USB containing the software will be shipped back to the sponsor.

At the end of the study all of the subjects will return the hearing aids to the sites. The sites will return the hearing aids back to the sponsor. It will be noted in the documentation that the devices were returned.

# 9. STUDY ASSESSMENTS

9.1 Study flow chart(s) / table of	or study procedur	es and assessme	ents
Study Periods	Intervention Period		
Visit	Screening/1	2	3
Day	0	10 +/- 5 days	20 +/- 5 days
Patient Information and Consent	Х		
Demographics	х		
Medical History	х		
In-/Exclusion Criteria	х		
Randomization	х	x	
Otoscopy	х	x	х
Audiometry	х		
Administer Medical Device	X*	X*	
Baseline Measure (Gothenburg questionnaire)	x		
Primary Variable (IOI-HA questionnaires)	x	x	
Secondary Variables (audiometry)	x		
Other Variables (speech testing)		x	х
Other Variables (product questionnaire)	х	x	
Other Variables (preference questionnaire)			x
Adverse Events	x	x	х

### 9.1 Study flow chart(s) / table of study procedures and assessments

\*Depending on randomization subjects will be fit with IMD at the first or second visit. Everyone will use the IMD at the first visit to perform audiometry.

### 9.2 Assessments of out comes

#### 9.2.1 Assessment of primary outcome

The primary outcome is the subjective assessment of the IMD compared with the RMD. It will be measured two times during the trial. After each field trial when the subjects have worn the devices programmed with either the RMD or the IMD they will answer 2 questionnaires (IOI-HA and product) that measure their subjective opinion of the benefit they received from the hearing aids during that period of the trial. The results from the two trial periods will directly compare the IMD with the RMD. At the final visit they will answer one preference questionnaire where they will choose between the hearing aids fitted with the IMD or the RMD.

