#### 9.3.3 Third Visit

Visit 3, Day 20 +/-5: Otoscopy is performed. The subjects will hand in the completed questionnaires given to them at the previous appointment. The investigator will review the questionnaires and inquire about AEs. Any AEs will be reported in the CRFs. A lab test will be made to test speech intelligibility with the FST.

The subjects will return the hearing aids. The subjects will complete a custom preference questionnaire about the experience with both field test periods. They will report which period of the field trial that they preferred.

They will be given the option to purchase hearing aids from the clinic where they were recruited.

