### 11.2 Determination of Sample Size

A literature search about this tested topic does not provide enough strong references to build a confirmatory analysis. It seems that results might be strongly influenced by the inclusion criteria (first time vs experienced hearing aid users) or test design (cross-over, multi-investigator, or between group designs). There is no article to our knowledge that includes a multi-investigator effect in the test design when looking at the effect of different fitting procedures. Adding a -by investigator- treatment interaction term seems to be mandatory if this trial wants to be determine the effect that different investigators have on the fitting procedure.

The sample size cannot be computed on reported effect sizes from previous experiment; however, the following summary shall be used as an indication to determine the sample size for participants per investigator:

•Naylor et al. (2015) about the narrative effect during the fitting with 24 experienced users and 16 first time users,

•Humes et al. (2017) about the performance with over-the-counter hearing aids compared to audiology best practice with 154 participants,

•Dawes et al. (2013) about the placebo effect in hearing aid trials with 16 experienced hearing aid users,

•Dawes et al. (2011) about the placebo effect in hearing aid trials with 20 experienced hearing aid users.

A placebo effect was found with sample sizes of about 20 participants in a single site study design. Adding an investigator effect in the design might bring new insights in this domain but requires a minimum number of participants per investigator to reduce imbalance between them.

With an effect size of 0.65 from the literature review, 2 degrees of freedom, 24 participants, and an alpha of 0.05, we can achieve a power of 0.82. Therefore, a minimum of 24 participants will be included in the trial overall. There will be 4 investigators with 6 to 8 participants per investigator.

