2.1 Primary outcomes

The perceived benefit will be measured with:

- a. the IOI-HA questionnaire and its official translation into German (Cox et al., 2002)
- b. a custom questionnaire based on reference article from Naylor et al. (2015).

These two questionnaires were used in the reference article from Naylor et al. (2015) to measure the effect of narrative embodied in the hearing aid fitting process. Even current research question addresses another aspect of the fitting process, these tools have shown a potential to detect changes in the investigated processes.

IOI-HA questionnaire

Perceived benefit of amplification assessed with 7 questions on a 5 points scale (maximum score 35). Indication from reference study found an effect of fitting process between the preferred and less preferred possibility:

- significant 3.2 scale points and an effect size of 0.68 with experience hearing aid users (n = 24),
- non-significant 0.5 scale points with first time hearing aid users (n = 16).

Custom questionnaire

From the reference study, the questionnaire will directly ask about the preference (much better/slightly better/no difference), the certainty of preference (10 points VAS), and the reason (multiple choice: sound quality, speech intelligibility, listening effort, comfort, loudness, other).

- Fitting procedures: no significant difference between both fitting procedures for first time and experienced hearing aid users,
- Placebo effect: 20 out of 24 indicated a difference with a mean certainty of 7.9/10 for the experienced users group. 14 out of 16 indicated a difference with a mean certainty of 7.0/10 for the first time users group

Order effect

From the reference study, test order might play a different role for first time or experienced users:

- No order effect was found with the experienced hearing aid users,
- A highly significant test order effect in favor for the second tested hearing aid was found for the first time users.

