3.2 Power analysis

The expected power as a function of the effect size can be computed with G*Power (version 3.1.9.2).

Preference: χ^2 distribution can be used to investigate if the preference distribution is due to chance or to the manipulated effect. We can compute the effect size from the reported literature with Cohen's w (Cohen, 1988):

$$W = \sqrt{\frac{(p_{0i} - p_{1i})^2}{p_{0i}}}$$

where p_{0i} is the value of the *i*th cell under H0 and p_{1i} is the value of the *i*th cell under H1. However, there are two possible analysis options that can be differentiated by the counting method.

1. with 2 outcomes i.e. there is an audible difference or not,

Naylor (2015) experiment 1: w = 0.67Naylor (2015) experiment 2: w = 0.75Naylor (2015) experiments 1 and 2: w = 0.7Dawes (2011) experiment 1: w = 0.5Dawes (2013) experiment 2: w = 0.5Dawes experiments 1 and 2: w = 0.5All the experiments together: w = 0.6

With an effect size of 0.6, 1 degree of freedom, 24 participants and α of 0.05, we can achieve a power of 0.84. This analysis method is used by Dawes in his papers because only one device was preferred over the other if the listeners had a preference. The influence of effect size variation on the achieved power is show in figure 1.

This analysis allows to answer the question is there is a difference between both method used in the test. But it does not give an indication about the preferred method.

2. with 3 outcomes i.e. preference for A, preference for B, or no preference,

Naylor (2015) experiment 1: w = 0.54Naylor (2015) experiment 2: w = 0.47Naylor (2015) experiments 1 and 2: w = 0.5Dawes (2011) experiment 1: w = 0.94Dawes (2013) experiment 2: w = 0.94Dawes experiments 1 and 2: w = 0.94all the experiments together: w = 0.65

With an effect size of 0.65, 2 degrees of freedom, 24 participants and α of 0.05, we can achieve a power of 0.82. The influence of effect size variation on the achieved power is show in figure 2.

Adding a degree of freedom in the analysis leads to a small loss of power, even if it is always higher than 80%. However, it might give more information about which method will be preferred.

[figure not shown]

Figure 1: Expected power as a function of the effect size with analysis on 2 levels (audible difference or not)

[figure not shown]

Figure 2: Expected power as a function of the effect size with analysis on 3 levels (preference for A, preference for B or no preference)

4. Analysis

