4.1 Analysis methods

Linear mixed effect regression will be used on the IOI-HA questionnaire, chi2 distribution on the preference test and paired t-test on audiometrical thresholds. Principal component analysis will be made on different outcomes and explanatory variables combinations.

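### The protocol visit text describes the preference question without a neutral answer, while the SAP's response scale, both its counting options and the 0.82 power all need one

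*Protocol*

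**What the plan says.** The preference question is described in three places.

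- Protocol 9.2.1: "they will answer one preference questionnaire where they will choose between the hearing aids fitted with the IMD or the RMD".
- Protocol 9.3.3, third visit: "They will report which period of the field trial that they preferred".
- SAP 2.1, custom questionnaire: "the questionnaire will directly ask about the preference (much better/slightly better/no difference").

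The SAP then counts the answers in one of two ways (3.2): "with 2 outcomes i.e. there is an audible difference or not", or "with 3 outcomes i.e. preference for A, preference for B, or no preference". Its power statement for the first is "With an effect size of 0.6, 1 degree of freedom, 24 participants and α of 0.05, we can achieve a power of 0.84". The second carries a power of 0.82, which protocol 11.2 repeats as its sample-size justification: "With an effect size of 0.65 from the literature review, 2 degrees of freedom, 24 participants". The analysis section (SAP 4.1) prescribes only "chi2 distribution on the preference test" and does not say which cells or which null. Protocol 11.4.2 bases the preference form on the reference study's questionnaire. The form itself is not reproduced in the text available.

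**The concern.** A choice between two fittings and a scale with a neutral point are different instruments. Both SAP counting options have a cell for participants who notice no difference or have no preference. A two-way form would leave that cell empty by construction, and a test of equal cells would then react to the empty cell whatever participants preferred.

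This bears on research question 1. The two fittings are programmed to be acoustically the same (protocol 6.1 and 8.1.2), so 'no difference' is the natural answer if there is no narrative effect. A form without it turns each indifferent participant into a vote for one method.

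**Working it through.** **1. Inputs.** n = 24 and alpha = 0.05 (protocol 11.2, SAP 3.2). Critical values are 3.84 (1 df) and 5.99 (2 df). The SAP gives the formula for Cohen's w but no numerical cell probabilities under H0.

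**2. Stated power.** Noncentral chi-square with noncentrality n·w²:
- w = 0.6, 1 df: 24 × 0.36 = 8.64, power 0.836 (stated 0.84).
- w = 0.65, 2 df: 24 × 0.4225 = 10.14, power 0.821 (stated 0.82).

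Both reproduce.

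**3. The null.** Equal cells recover the SAP's effect sizes for the individual studies.
- Two cells, 1/2 each: 20 of 24 gives 0.667 (SAP 0.67); 14 of 16 gives 0.75 (SAP 0.75); 75% gives 0.50 (SAP 0.5).
- Three cells, 1/3 each: 75/0/25 gives 0.935 (SAP 0.94). For the reference study, splits of 14/6/4 and 8/6/2 give 0.54 and 0.47, as in the SAP. These splits are back-solved from w and the neutral counts; the documents do not report them.

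The pooled three-cell value came out at 0.66 rather than 0.65 (counts 49/12/15). That small gap does not affect what follows.

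**4. Two-way form, SAP counting, n = 24.**
- Difference or not: observed 24 and 0, expected 12 each. Chi-square = 12²/12 + 12²/12 = 24, p about 1e-6, for every split.
- Three cells: observed a, b and 0 with a + b = 24, expected 8 each. Chi-square = 3(a² + b²)/24 − 24. The minimum is at 12:12: 3 × 288/24 − 24 = 12.0, p = 0.0025. The maximum, at 24:0, is 48.

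All 25 possible splits reject under both options. The same holds at n = 28, 32 and 40.

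**5. Neutral answer allowed, IMD and RMD equally preferred, n = 24.** Exact enumeration of rejection probability. The neutral rates are assumptions; 16.7% matches the reference study's 4 of 24.

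| Neutral rate | Difference or not | Three cells | IMD v RMD, 50:50, among those with a preference |
|---|---|---|---|
| 10% | 0.998 | 0.67 | 0.054 |
| 16.7% | 0.96 | 0.33 | 0.054 |
| 33% | 0.42 | 0.05 | 0.049 |

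A single data set shows the same. A 10:10:4 result gives 3(100 + 100 + 16)/24 − 24 = 3.0 on three cells (p = 0.22), but 20 against 4 gives 8²/12 + 8²/12 = 10.67 on two cells (p = 0.001).

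**6. Power of the IMD-versus-RMD test (1 df).**
- Neutrals set aside, 14:6 among 20: noncentrality 20 × 0.4² = 3.2, power about 0.43.
- Two-way form, neutrals split evenly, 16:8 among 24: 24 × (1/3)² = 2.67, power about 0.37.
- Two-way form, 9:7 proportions at n = 24: 24 × 0.125² = 0.375, power about 0.09.

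None is near 0.82.

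**The case against.** Only SAP 2.1 sets out answer categories. Protocol 9.2.1 and 9.3.3 are one-sentence descriptions that do not rule out a neutral answer. Protocol 11.4.2 points to the reference questionnaire, which SAP 2.1 describes as having one, and the 2 df in protocol 11.2 require three cells. The study is declared exploratory, and the schedule lists preference among the other variables, although SAP 2.1 places the custom questionnaire under primary outcomes. All of this stands. It makes a three-answer form the likelier intention and limits the weight of the point.

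A reader might infer that the preference test is bound to reject in this trial. The documents do not support that. It would require a two-way form, the inferred equal-cell null, and an analyst who keeps the structurally empty cell. Software that drops that cell would compare IMD with RMD, and SAP 4.1 does not exclude this, though no section names it.

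A reader might also infer that asking by period biases the answer, since SAP 2.1 reports an order effect in first-time users. Period identifies fitting once the sequence is known, and the crossover is balanced for order, so the documents do not establish such a bias.

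It can fairly be said that the equal-cell null is the larger fault, because a neutral answer reduces the false signal without removing it. Step 5 bears this out, so aligning the wording cannot be the whole remedy.

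**Conclusion.** The inconsistency is real and should be resolved before the form is used. The protocol visit text omits a category on which the SAP's response scale, both counting options and the 0.82 depend. Certain rejection at n = 24 follows only if the form is two-way and the equal-cell null is applied with the empty cell retained; the null is inferred, not stated.

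The second part does not depend on how the form is worded. With a neutral answer available and no IMD/RMD preference at all, the SAP's options reject with probability 0.42 to 0.998 (difference or not) and 0.05 to 0.67 (three cells) over assumed neutral rates of 33% down to 10%. A significant result on either would not by itself show that one fitting is preferred.

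**What to change.** 1. Align protocol 9.2.1, 9.3.3 and the preference form with the SAP 2.1 scale: much better or slightly better for either fitting, and no difference. State that 'no difference' is valid data and not a missing value.
2. In the analysis, identify each answer by fitting (IMD or RMD), using the sequence if the question is asked by period.
3. In SAP 4.1, name IMD versus RMD against 50:50, among participants with a preference, as the preference test (size about 0.05). Report the neutral proportion descriptively.
4. In protocol 11.2 and SAP 3.2, state that the 0.82 does not apply to this test, and give its power under stated splits.

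If a two-way form is kept, both counting options should be deleted and items 3 and 4 still apply, without the neutral proportion.

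The cost is a few sentences and a check of the form, with no extra participants or visits. The downside is that neutral answers reduce the number informative for IMD versus RMD, and the stated power becomes less favourable.
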